### **9.3.1 Overall Summary of AEs**

An overall summary of AEs will be presented by dose group and will reflect a count of TEAEs, treatment-emergent serious adverse events (SAEs), TEAEs by relationship to investigational product, and TEAEs by severity. Additionally, the table will reflect the count and percentage of subjects experiencing the following: any TEAEs, SAEs, TEAEs leading to treatment discontinuation, TEAEs resulting in death, TEAEs classified as pulmonary exacerbations (investigator and protocol-defined), TEAEs classified by relationship to investigational product, TEAEs classified by relationship to nebulization/treatment administration, and TEAEs by severity. The overall summary of AEs will be presented for the overall time period for each study part, as well as for the study overall. The overall summary of AEs will also be presented for the overall time period and through 1 month post-dose (Day 29, Day 57, and Day 32 for Part A, Part B, and Part D, respectively) by pooled treatment group. All percentages will use the number of subjects in the safety analysis set as the denominator.

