When the fourth subject in the dose group (Groups 1 and 2) has completed at least 1 week of safety follow-up after the third dose, the PSRC will review the blinded safety data for the 4 subjects in the group. The PSRC will also review the blinded safety data for the Part A subjects who received a single dose of the next higher dose level to be escalated to. Similar to Part A, if no dose limiting toxicity has been observed and there are no safety concerns for the dose group overall, the enrollment and treatment of subjects at the next higher dose level will be initiated.

In both Parts A and B of the study, escalation to the next higher dose level may not proceed if 2 or more subjects at the current dose level experience a Grade 3 (severe) treatment-emergent AE that is assessed as both clinically significant (based on the nature and duration of the toxicity) and probably or definitely related to IP by the Investigator. The PSRC will review these treatment-emergent AEs along with all available safety data to determine if dose escalation can proceed or will be stopped due to dose limiting toxicity. Other scenarios, which include but are not limited to the occurrence of possibly related Grade 3 (severe) treatment-emergent AEs, or probably or definitely related Grade 2 (moderate) treatment-emergent AEs that are judged as clinically significant, will be reviewed and assessed on a case-by-case basis by the PSRC.

If deemed necessary by the PSRC, a dose group may be repeated in a new group of subjects to further assess the safety of the dose level prior to dose escalation in Part A or to further assess the tolerability of the dose level before deciding to advance it from single dosing in Part A to multiple dosing in Part B (see below).

The PSRC may request unblinding the treatment assignment(s) for an individual subject or for the entire dose group to help clarify decisions to dose escalate, to repeat a dose group, or to initiate Part B (Section 6.2.3).

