9.8.1. Safety Analyses

Full details of the safety analyses will be provided in the statistical analysis plan.

Subject disposition, demographics and baseline characteristics, IP exposure, and prior and concomitant medications will be summarized. Adverse events will be coded using the MedDRA. The number and percentage of subjects with treatment-emergent AEs will be calculated overall, by system organ class, by preferred term, and by treatment group. Treatment-emergent AEs will be further summarized by severity and relationship to IP. Adverse events related to IP, AEs leading to withdrawal, SAEs, and deaths will be similarly summarized or listed. The number and incidence of pulmonary exacerbations will be analyzed by treatment group. Results from vital sign measurements, clinical laboratory tests, ECGs, spirometry testing, pulse oximetry, and chest x-rays will be summarized by treatment, dose group, and visit. Clinically important findings will also be summarized or listed.

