## **2.5 Sample Size Determination**

The sample size is not based on any statistical considerations. Instead, the sample size is based on traditional phase 1 first-in-human study designs for this disease population. In Parts A and B of the study, the inclusion of 4 subjects per dose group (3 subjects randomized to MRT5005 and 1 subject randomized to placebo) will provide basic information on safety and tolerability during dose escalation of MRT5005. In Part D, 8 subjects treated at 4 mg MRT5005 or placebo (6 subjects randomized to MRT5005 and 2 subjects randomized to placebo) will provide further safety and tolerability data on MRT5005. This study is also designed with the flexibility to enroll additional groups of subjects to support meeting its objectives.

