### 9.3 Adverse Events

Adverse events will be coded using the Medical Dictionary for Regulatory Activities (MedDRA) Version 23.1 to identify the system organ class and preferred term.

Treatment-emergent AEs are defined as events that are newly reported or reported to worsen in severity after the start of treatment. Adverse events that occur after the treatment start date, occur on the treatment start date with a time that is equal to or after treatment start time, or that have a missing AE start date will be categorized as treatment-emergent. Treatment-emergent AEs will be summarized for the safety analysis set.

For summaries of TEAEs by time interval, the categorizations for Part A will be: Overall, Study Day 1, 1 < Study Day ≤ 7, 1 ≤ Study Day ≤ 29, and Study Day > 29. The categorizations for Part B will be: Overall, Study Day 1, 1 < Study Day ≤ 7, 1 ≤ Study Day ≤ 36, 1 ≤ Study Day ≤ 57, and Study Day > 57. The categorizations for Part D will be: Overall, Study Day 1, 1 < Study Day ≤ 5, 1 ≤ Study Day ≤ 11, 1 ≤ Study Day ≤ 32, and Study Day > 32. The categorizations for the study overall will be: Overall, through 1 month post-dose (Day 29, Day 57, and Day 32 for Part A, Part B, and Part D, respectively), after 1 month post-dose (> Day 29, > Day 57, and > Day 32 for Part A, Part B, and Part D, respectively). Any TEAE with a completely missing start date will not be categorized into a specific time interval, but will be included in the Overall category.

Any dose limiting toxicities identified will be addressed in the clinical study report (CSR).

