**Adverse Events**

Table 14.3.1.1 (AE\_TAA\_F\_X)  
Overall Summary of Treatment-Emergent Adverse Events by Dose Group  
Population: Safety Analysis Set

Part: x	MRT5005 Xmg N=xx n (%)	MRT5005 Xmg N=xx n (%)	MRT5005 Xmg N=xx n (%)	Pooled Placebo N=xx n (%)
Number of TEAEs Reported	xx	xx	xx	xx
Number of Subjects with Any TEAE Reported [1]	xx (xx.x)	xx (xx.x)	xx (xx.x)	xx (xx.x)
Number of Serious TEAEs Reported	xx	xx	xx	xx
Number of Subjects with Any Serious TEAE Reported [1]	xx (xx.x)	xx (xx.x)	xx (xx.x)	xx (xx.x)
Number of TEAEs by Relationship to IP				
Not Related	xx	xx	xx	xx
Related	xx	xx	xx	xx
Number of Subjects with TEAEs by Relationship to IP [2]				
Not Related	xx (xx.x)	xx (xx.x)	xx (xx.x)	xx (xx.x)
Related	xx (xx.x)	xx (xx.x)	xx (xx.x)	xx (xx.x)
Number of Subjects with TEAEs by Relationship to Nebulization/Treatment Administration [3]				
Not Related	xx (xx.x)	xx (xx.x)	xx (xx.x)	xx (xx.x)
Related	xx (xx.x)	xx (xx.x)	xx (xx.x)	xx (xx.x)
Number of TEAEs by Severity				
Mild	xx	xx	xx	xx
Moderate	xx	xx	xx	xx
Severe	xx	xx	xx	xx
Number of Subjects with TEAEs by Severity [4]				
Mild	xx (xx.x)	xx (xx.x)	xx (xx.x)	xx (xx.x)
Moderate	xx (xx.x)	xx (xx.x)	xx (xx.x)	xx (xx.x)
Severe	xx (xx.x)	xx (xx.x)	xx (xx.x)	xx (xx.x)
Number of Subjects with TEAEs Leading to Treatment Discontinuation [1]	xx (xx.x)	xx (xx.x)	xx (xx.x)	xx (xx.x)
Number of Subjects with TEAEs Resulting in Death [1]	xx (xx.x)	xx (xx.x)	xx (xx.x)	xx (xx.x)
Number of TEAEs Classified as a Pulmonary Exacerbation by Type				
All	xx	xx	xx	xx

Investigator-Defined	xx	xx	xx	xx
Protocol-Defined	xx	xx	xx	xx
Number of Subjects with TEAEs Classified as a Pulmonary				
Exacerbation by Type [1]				
All [5]	xx (xx.x)	xx (xx.x)	xx (xx.x)	xx (xx.x)
Investigator-Defined	xx (xx.x)	xx (xx.x)	xx (xx.x)	xx (xx.x)
Protocol-Defined	xx (xx.x)	xx (xx.x)	xx (xx.x)	xx (xx.x)

AB\_F03

[1] AE\_F05  
[2] AE\_F06a  
[3] AE\_F06b  
[4] AE\_F07  
[5] AE\_F06d  
PC\_F02

Listing Source: AE\_LAA\_F\_X

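### The TEAE tables never cross severity with relationship to IP, so they cannot give, by dose group, the number of subjects with a severe event rated probably or definitely related

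*SAP*

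**What the plan says.** Protocol 8.1.2 has the Investigator rate causality on four levels: not, possibly, probably or definitely related. Protocol 8.1.1 grades severity from 1 to 5. Protocol 3.4.2 joins the two on a single event. Escalation may not proceed if 2 or more subjects at the current dose "experience a Grade 3 (severe) treatment-emergent AE that is assessed as both clinically significant" and probably or definitely related to IP. Possibly related Grade 3 events go to the Protocol Safety Review Committee (PSRC) case by case.

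Protocol 9.8.1 promises that TEAEs will be summarized further by severity and by relationship, and adds: "Adverse events related to IP, AEs leading to withdrawal, SAEs, and deaths will be similarly summarized or listed". SAP 12 records no change to the planned analyses.

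SAP 9.3.1 lists "TEAEs by relationship to investigational product, and TEAEs by severity" among the overall counts. That sentence shows only two separate classifications; the reduction to two causality rows is in the shells for Tables 14.3.1.1 and 14.3.1.1.2 (14.3.1.1.1 repeats the first). Footnote AE_F06a places a subject in one relationship row, by the event rated nearest to the drug, and treats a missing rating as Related. Footnote AE_F07 places a subject in one severity row, by the worst event, and treats a missing grade as Severe.

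The shells for TEAEs, SAEs and AESIs by SOC and preferred term, and the exacerbation table, carry neither variable. The febrile and hypersensitivity tables carry severity only. On dose-limiting toxicity, SAP 9.3 says: "Any dose limiting toxicities identified will be addressed in the clinical study report (CSR".

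**The concern.** The primary objective is the safety and tolerability of escalating doses. The protocol's own marker of poor tolerability needs grade and causality together on one event, and it separates possibly related from probably or definitely related. The planned tables keep grade and causality apart and appear to merge the last three causality levels.

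A dose group can then show subjects in the Severe row and subjects in the Related row while no table says whether any severe event was related, or how firmly. AEs are collected to Day 337, 365 or 341 whatever their cause, so the severe event and the related event need not be the same one. What is at stake is the dose-group summary in the study report.

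**Working it through.** The plan states no figure to reproduce: SAP 2.5 says "The sample size is not based on any statistical considerations". The check applies the SAP counting rules to one Part A or Part B dose group.

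**Inputs.** Active subjects per group: 3 (SAP 2.5, "3 subjects randomized to MRT5005 and 1 subject randomized to placebo"). Relationship rows: 2 (Table 14.3.1.1 shell). Severity rows: 3 (same shell). Collected causality levels: 4 (Protocol 8.1.2). Counting rules: AE_F06a and AE_F07. Target count: subjects with at least one severe (Grade 3) event rated probably or definitely related.

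**Step 1. Two kinds of subject, each with two events.**

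| Subject type | Event 1 | Event 2 | Relationship row | Severity row | In target count? |
|---|---|---|---|---|---|
| A | severe, not related | mild, probably related | Related | Severe | no |
| B | severe, probably related | mild, not related | Related | Severe | yes |

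Each type adds the same amounts to every row: 2 TEAEs, 1 related and 1 not related event, 1 mild and 1 severe event, 1 Related subject, 1 Severe subject. A group with k subjects of type B and 3 − k of type A therefore always prints 6 TEAEs, 3 related and 3 not related events, 3 mild and 3 severe events, 3/3 Related and 3/3 Severe. The target count is k, so 0, 1, 2 and 3 all fit the same table. This step needs no assumption about where possibly related falls.

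**Step 2. The effect of two causality levels.** Type C has severe, possibly related plus mild, not related. If possibly related counts as Related, three type C subjects print the same rows again, with a target count of 0. Crossing severity with the two-level variable would separate A from B but not B from C. Both the cross and the four levels are needed.

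**Step 3. How general this is.** There are 3 × 4 = 12 kinds of event, 12 × 13 / 2 = 78 unordered pairs of events for a subject, and 80 × 79 × 78 / 6 = 82,160 groups of three such subjects. With possibly related counted as Related, these give 500 distinct sets of table rows:

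- 360 do not fix the target count. In the other 500 − 360 = 140 it is fixed at 0.
- 175 do not settle whether 2 or more subjects are in the target count. The other 500 − 175 = 325 rule it out; none confirms it.

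The last result follows from the pooling: any related event could have been only possibly related, so 0 is always compatible. These are counts of possible patterns, not probabilities.

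**The case against.** The strongest answer is that the information is already planned. Listing 16.2.7.1 is produced by dose group with severity and relationship on the same event row, and Listings 16.2.7.7 and 16.2.7.8 do the same around dosing. With 3 active subjects per group, a reader can find a severe related event by eye. Protocol 9.8.1 allows related AEs to be summarized or listed, and it does not promise a cross-tabulation. This stands: the data are not lost, and 9.8.1 is met, though only as separate marginal counts. The listing shell does not say how many causality levels it prints.

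A reader might also infer that escalation was exposed to error. The documents do not support that. Protocol 3.4.1.1 and 3.4.2 give those decisions to the PSRC, which reviews blinded safety reports including AE listings during the study.

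A further tempting inference is that the plan fails to count the trial's dose-limiting toxicities and that a new row would count them. Neither part holds. The criterion requires an event "assessed as both clinically significant (based on the nature and duration of the toxicity) and probably or definitely related to IP by the Investigator", the AE listing shell has no column for clinical significance, and the PSRC decides what is dose limiting. SAP 9.3 sends any identified case to the study report.

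Other planned displays narrow the gap. Table 14.3.1.1.1 stops at Day 29, 57 or 32, which limits late unrelated events. Febrile and hypersensitivity reactions have severity by dose group, and AESIs are moderate-to-severe and possibly related by definition. The protocol's dose rationale (2.2.3) describes the febrile reactions seen by then as mild to moderate; a group with no severe event has a joint count of 0 without further work. The documents give no rate of unrelated severe events, so none is assumed here.

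**Conclusion.** The point holds as a gap in the summary tables. By dose group, the planned tables cannot give the number of subjects with a severe event rated probably or definitely related; identical rows fit any value from 0 to 3 of 3 active subjects. That range rests only on the shells and the two counting footnotes. The pattern counts also assume two events per subject and that possibly related is tabulated as Related. The second assumption is the natural reading of the shell, but it is stated nowhere.

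It does not follow that data are missing, that any dose decision was affected, or that the protocol's analysis commitment is broken. This is an inexpensive improvement to how the primary tolerability result is reported. A related omission is that the severity rows stop at Severe, while Protocol 4.5.6 makes a probably or definitely related Grade 4 event a study stopping criterion.

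**What to change.** 1. In Tables 14.3.1.1 and 14.3.1.1.1, by dose group, add severity (including Grades 4 and 5) crossed with the four collected relationship categories, at subject and event level. Take grade and causality from the same event. Count a subject in a cell when at least one event has both that grade and that rating. Add the same rows to the pooled Table 14.3.1.1.2 for completeness.
2. State how the four levels map to Related and Not Related, and where an event with a missing rating goes on the four-level scale.
3. Add one table of related TEAEs by SOC, preferred term and maximum severity, by dose group.
4. Label the new rows as severity-by-relationship counts. Adjudicated dose-limiting toxicities remain a PSRC judgment, reported in the study report.

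The cost is SAP wording, extra shell rows and one added table. Severity and relationship are already collected for every event, so no new data are needed. No escalation or stopping rule changes.

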### **9.3.2 Subject-level and Event-level Summary of AEs**

A summary table will be presented for each study part by dose group to reflect a count and percentage of subjects experiencing at least 1 TEAE in each system organ class and preferred term and a count of TEAEs occurring in subjects in the safety analysis set within each system organ class and preferred term. All percentages will use the number of subjects in the safety analysis set as the denominator. Therefore, if a subject has more than 1 AE within a system organ class, the subject will be counted only once in that system organ class. If a subject has more than 1 AE that codes to the same preferred term, the subject will be counted only once for that preferred term. For the event-level summaries, subjects experiencing more than 1 AE within a system organ class or preferred term will be counted more than once for that system

organ class or preferred term. Tabular summaries will be sorted by descending overall (MRT5005 + Placebo) frequency in subject counts by system organ class and by preferred term.

Using the same subject-level and event-level counting rules, a summary table of TEAEs by preferred term will be presented for the overall time period by dose group for each study part, as well as separately through Day 29, Day 57, and Day 32 for Part A, Part B, and Part D, respectively. In addition, the summary of AEs by preferred term will be presented for the study overall for the overall time interval and through 1 month post-dose (Day 29, Day 57, and Day 32 for Part A, Part B, and Part D, respectively) by pooled treatment group.

All AEs will be presented in data listings for subjects in the safety analysis set, including a flag to distinguish if the AE was treatment-emergent.

#### **9.4 Deaths, Serious Adverse Events, and Other Significant Adverse Events**

Treatment-emergent SAEs and adverse events of special interest will be summarized for all subjects in the safety analysis set for each study part by dose group and time interval.

Summary tables will be presented by dose group to reflect a count and percentage of subjects experiencing at least 1 TEAE in each system organ class and preferred term (subject-level analysis) and a count of TEAEs (event-level analysis) occurring in subjects in the safety analysis set within each system organ class and preferred term within each AE subset (serious, AESIs). All percentages will use the number of subjects in the safety analysis set as the denominator. Therefore, for the subject-level analysis, if a subject has one or more AE within a system organ class, the subject will be counted only once in that system organ class. If a subject has one or more AE that codes to the same preferred term, the subject will be counted only once for that preferred term. For the event-level analysis, subjects experiencing more than 1 AE within a system organ class or preferred term will be counted according to the number of AEs they experience (more than once) for that system organ class or preferred term. Tabular summaries will be sorted by descending overall (MRT5005 + Placebo) frequency in subject counts by system organ class and by preferred term.

Using the same subject-level and event-level counting rules, treatment-emergent pulmonary exacerbations (investigator and protocol-defined) will be summarized by preferred term for all subjects in the safety analysis set for each study part by dose group and time interval.

Treatment-emergent febrile reactions and hypersensitivity reactions will be presented as a count of febrile reactions, febrile reactions by severity, hypersensitivity reactions, and hypersensitivity reactions by severity. Additionally, the table will reflect the count and percentage of subjects experiencing the following: any febrile reaction, any febrile reaction by severity, any hypersensitivity reaction, and any hypersensitivity reaction by severity. The summary will be for all subjects in the safety analysis set by dose group for each study part. In addition, the summary of treatment-emergent febrile reactions and hypersensitivity reactions will be presented for all subjects in the safety analysis set for the study overall by pooled treatment group. Febrile reactions will be identified based on a preferred term of body temperature increased or preferred term of pyrexia within the 24 hours after completion of

nebulization on any dosing day with at least one other systemic symptom reported as a preferred term of headache, arthralgia, myalgia, fatigue, chills, nausea, or vomiting within the 24 hours after completion of nebulization on any dosing day. Severity grade for febrile reactions will be based on the maximum severity of the preferred terms comprising the febrile reaction. Hypersensitivity reactions will be identified based on a preferred term of hypersensitivity within the 24 hours after completion of nebulization on any dosing day.

Adverse events leading to withdrawal from treatment, AEs resulting in death, pulmonary exacerbations (investigator and protocol-defined), adverse events of special interest, and SAEs will be presented in data listings for subjects in the safety analysis set. Adverse events of pyrexia or body temperature increased during nebulization or within the 24 hours after completion of nebulization on any dosing day will also be listed for subjects in the safety analysis set. This listing will include all adverse events that occurred during nebulization or within the 24 hours after completion of nebulization for subjects that had an adverse event of pyrexia or body temperature increased during nebulization or within the 24 hours after completion of nebulization on any dosing day. All adverse events that occurred during nebulization or within the 24 hours after completion of nebulization will also be listed for subjects in the safety analysis set. Febrile reactions and hypersensitivity reactions within the 24 hours after completion of nebulization on any dosing day will also be listed for subjects in the safety analysis set. This listing will include all adverse events that meet the specified febrile reaction or hypersensitivity criteria that occurred within the 24 hours after completion of nebulization for subjects that had a febrile reaction or hypersensitivity reaction within the 24 hours after completion of nebulization on any dosing day.

